#### 1) Unintended consequences:

**a. Patient fall rates:** All patient falls are reported and recorded as a part of the VUH quality program using the National Database of Nursing Quality Indicators (NDNQI) definitions and process. As per NDNQI, a fall is defined as "an unplanned descent to the floor or other lower surface with or without injury to the patient that occurs in an eligible nursing unit." All events are reviewed and categorized based on the degree of patient injury/harm, if any occurred. The fall rate per 1,000 patient days for the aggregate study unit population will be measured. In addition the rate of falls with harm (as defined by NDNQI) will also be assessed.

**b.** Fall events in patients placed in the preemptive intervention: In addition to the aggregate fall rates for the study units, the frequency and number of falls (as defined by NDNQI) that occur in patients placed into preemptive isolation will be captured.

**c. HCP contact with patients placed in the preemptive intervention**: Trained study personnel will audit HCP contact (time spent, # of encounters) for all patients placed into preemptive isolation as previously described. As a proxy of HCP frequency of contact, the number of vital signs recorded per patient day will also be analyzed.

MDRO Type	Defined as
MRSA	Staphylococcus aureus resistant to oxacillin or methicillin by standard susceptibility testing methods
VRE (vancomycin- resistant enterococci)	Enterococcus faecalis, Enterococcus faecium, or other Enterococcus species that is resistant to vancomycin
CRE (carbapenem- resistant Enterobacteriaceae)	Any Escherichia coli, Klebsiella oxytoca, Klebsiella pneumoniae, or Enterobacter spp. testing resistant to imipenem, meropenem, doripenem, or ertapenem by standard susceptibility testing methods OR by production of a carbapenemase (i.e., KPC, NDM, VIM, IMP, OXA-48) demonstrated using a recognized test (e.g., polymerase chain reaction).
MDR (multidrug resistant)- Acinetobacter	Any Acinetobacter spp. testing non-susceptible (i.e., resistant or intermediate) to at least one agent in three or more classes of antibiotics (excluding nitrofurantoin, tetracyclines, 1st and 2nd generation cephalosporins, and non- extended-spectrum penicillins)
ESBL + GNB (extended-spectrum beta-lactamase producing gram- negative bacillus)	Any E. coli , K. pneumoniae and K. oxytoca demonstrated to have ESBL activity based on results from BD Phoenix through microdilution methodology. The BD Phoenix performs ESBL testing using cephalosporins (ceftazidime/cefotaxime/ceftriaxone) + clavulanic acid.

Table 3:	Definitions	of MDROs	Included in	Primar	y Study	y Outcome
----------	-------------	----------	-------------	--------	---------	-----------

2) Subgroup examinations of individual pathogen HO-infection rates for the overall study population and the aggregate HO-MDRO/*C. difficile* infection rate for each individual study unit

**Covariates:** Several factors may affect the impact of the intervention on the primary outcome. These will be measured and included in the analysis.

**1) Hand hygiene compliance:** Study unit compliance with hand hygiene as monitored by the Vanderbilt Hand Hygiene Program^34 will be included for analysis.

2) PPE compliance: Trained study personnel will perform audits of PPE use by HCP caring for patients placed into the preemptive intervention.

**3) Antimicrobial utilization:** Use of broad-spectrum antibiotics is currently tracked as a part of the VUMC Antibiotic Stewardship Program (Co-directed by Epicenter investigator [name]). Because antibiotic use is a factor in the acquisition of MDROs and *C. difficile*, we will include a measure of broad-spectrum antimicrobial use in the analysis (measured as days of therapy [DOT]).

**Analysis:** The rates of the primary and secondary outcomes will be compared for the following phases, defined *a priori*: 6 month baseline period, 6 month intervention period, and 6 month withdrawal period. In addition, a more robust interrupted time-series regression analysis with Newey-West standard errors will be performed using bimonthly outcome rates (which will provide 12 separate time point measurements for each period).

**Sample size considerations:** Existing data were used to assess sample size adequacy. Using patient-days, the mean patient days per period will be 4,952 patient days/month for a total of 29,710/period. The rate of HO-MDROs on the units of interest is 4.6/1000 patient days for an average of 137 evaluable events per period. This study will have 80% power to detect a true difference in infection rates of 1.4/1000 patient days. That means a reduction by approximately 42 events in the intervention period. Nursing home admissions (those that will receive the intervention) are at least 4.3-5.6% on target units which is likely an underestimate given the current reporting system.

**Safety:** A data safety monitoring board (DSMB) will be created to oversee any potential adverse events that would require further assessment and intervention. At present 100% of falls, including all falls with harm, have an event review as part of the VUH quality program. The current fall rate on the four proposed units is 2.6 falls/month. The DSMB will review the event analysis of all falls on the unit on a quarterly basis with more in depth interim analysis of all falls stratified by study intervention. Due to the low rates of baseline falls, there is the potential for low case counts to cause large percentage increases, making a pre-defined threshold difficult for stopping the trial. If a sustained, significant increase in falls is seen and thought to be due to the Contact Precautions intervention, then the study will be halted.

**Limitations and future directions:** The evaluation of preemptive Contact Precautions for patients with LTCF exposure will be conducted in an academic, tertiary referral hospital with high rates of hand hygiene compliance. Preemptive isolation is a supplementary strategy and may not be generalizable to acute care hospitals with suboptimal hand hygiene compliance. If an impact on HO infections is seen during the intervention without unintended consequences, then there may be other high risk epidemiologic groups that could benefit from preemptive isolation. If this trial shows a reduction in HO-MDRO rates, this strategy may benefit from a larger-multicenter trial with randomization. This study has the potential to transform how isolation policies are implemented in acute care hospitals and could reduce the risk of pathogen transmission to other HCP and their patients.

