#### **APPROACH:**

**Preliminary studies:** The Vanderbilt Epicenter investigators have experience in the conduct of operational quasi-experimental studies. Specifically, we recently conducted a successful pragmatic cluster randomized, crossover study of 9,340 patients admitted to 5 adult ICUs from July 2012 through July 2013 to assess if daily chlorhexidine (CHG) bathing reduced HAIs. The

[figure not shown]
primary prespecified outcome was a composite of central line-associated bloodstream infections (CLABSIs), catheter-associated urinary tract infections (CAUTIs), ventilator-associated pneumonia (VAP), and *C. difficile* infections. After adjusting for age, sex, race/ethnicity, unit of admission, time, comorbid conditions, and admission white blood cell count, no significant difference between groups in the rate of the primary outcome was detected. This study demonstrates Vanderbilt's capacity to support large-scale trials evaluating infection prevention interventions.

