#### **RESEARCH DESIGN AND METHODS:**

**Study design:** Pre-post withdrawal quasi-experimental study using interrupted time series analysis.

**Study sites:** Six inpatient medical units within Vanderbilt University Hospital will serve as study units. These have been selected due to a higher rate of HO-MDRO/*C. difficile* incidence and/or a higher proportion of admissions comprising LCTF patients. The proposed acute care units have an average of 4,952 patient days per month with LTCF residents comprising 4.3-5.6% of unit admissions. This percentage is likely an underestimation because not all places of patient origin are documented and transfers between units within VUH are not included in this analysis. The HO-MDRO/*C. difficile* rate of these 6 units combined was 4.62 per 1,000 patient days for 2014.

**Study procedures:** After a 6 month baseline period, all units will be transitioned to a 6 month intervention period where all patients transferred onto the study units with LTCF origin prior to admission will be placed on preemptive Contact Precautions (Figure 5). Both patients admitted directly to a study unit as well as patients transferred from a non-study unit onto a study unit will be included under the policy. A washout period of 2 weeks will be introduced before a post-intervention withdrawal period of 6 months is implemented.

Inclusion/exclusion criteria: All patients admitted to the unit will be included in the study. There will be no exclusion criteria.

**Primary outcome - Rate of hospital-onset MDRO and** *C. difficile* **infections:** Aggregate rates of all hospital-onset (HO)-MDRO infections (Table 3), including MRSA, *C. difficile*, VRE, ESBL+ GNB, CRE, and MDR *Acinetobacter*, on participating units will be calculated. As active surveillance for these pathogens is not performed at VUH, only culture specimens obtained for clinical decision making will be included. Specimens from any site (e.g. blood, urine, wound) will be included. These events will be captured daily using the Vanderbilt Infection Prevention Electronic Resource (VIPER), an HAI surveillance platform that monitors laboratory results in real time. Events will be classified as HO if the specimen was collected >3 days after admission to VUH (i.e. on or after day 4).

Secondary outcomes:

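### Aim III compares different patients across three phases without randomisation or concurrent controls, yet none of its named covariates is a patient characteristic fixed at admission

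*Protocol*

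**What the plan says.** The study design entry for Aim III reads "Pre-post withdrawal quasi-experimental study using interrupted time series analysis". Six medical units pass together through a baseline, an intervention and a withdrawal phase of six months each, with a two-week washout before withdrawal. On eligibility, "All patients admitted to the unit will be included in the study", and there are no exclusions.

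The Covariates paragraph opens with "Several factors may affect the impact of the intervention on the primary outcome. These will be measured and included in the analysis" and numbers three items:

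- Hand hygiene: "Study unit compliance with hand hygiene as monitored by the Vanderbilt Hand Hygiene Program".
- PPE compliance: "Trained study personnel will perform audits of PPE use by HCP caring for patients placed into the preemptive intervention".
- Antimicrobial use: "we will include a measure of broad-spectrum antimicrobial use in the analysis", measured as days of therapy.

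The Analysis paragraph says "The rates of the primary and secondary outcomes will be compared for the following phases", meaning baseline, intervention and withdrawal. It adds an interrupted time series with Newey-West standard errors and 12 points per period. Individual units appear only as a subgroup examination. The limitations paragraph covers generalisability and does not mention confounding between phases.

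Under Preliminary studies, the team's cluster-randomised crossover trial in five adult ICUs is reported as analysed "After adjusting for age, sex, race/ethnicity, unit of admission, time, comorbid conditions, and admission white blood cell count".

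**The concern.** Each phase holds an essentially new set of patients. If they differ between phases in age, comorbidity or distribution over the six units, the aggregate rate of hospital-onset infection changes whether or not preemptive isolation works. The analysis could then credit the policy with an effect it did not have, or miss one that it had.

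The covariates named in the protocol do not measure that mix at admission. In the randomised trial that the protocol offers as preliminary work, the team did adjust for it. The unrandomised design has the greater need and the thinner list, and no reason is given.

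Small drifts matter here because long-term care residents, the only patients isolated under the policy, are put at 4.3-5.6% of unit admissions (described as a likely underestimate). A modest change among the other patients could rival a plausible effect.

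**Working it through.** **1. The plan's own figures.** Sample size considerations gives 29,710 patient-days per period, a rate of 4.6 per 1,000, about 137 events, and 80% power for a difference of 1.4 per 1,000 (about 42 events). Alpha is not stated; I assume two-sided 0.05.

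- Events at baseline: 4.6 × 29.71 = 136.7. At the reduced rate: 3.2 × 29.71 = 95.1. Difference: 41.6.
- Power: Φ(41.6/√(136.7 + 95.1) − 1.96) = Φ(2.73 − 1.96) = 0.78. A two-proportion calculation gives 78.2%.

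The stated figures reproduce. The calculation is unadjusted and takes the two periods as alike in everything except the intervention.

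**2. Effect of a case-mix shift when the intervention does nothing.** The document gives no case-mix data, so these inputs are assumptions. Let a higher-risk group make up a share p of patient-days and have RR times the infection rate of the rest. The aggregate rate is proportional to p × RR + (1 − p). Start from p = 0.40. The standard error of the log rate ratio for two periods of 137 events is √(2/137) = 0.121. With z = |log ratio|/0.121, the two-sided rejection probability is Φ(z − 1.96) + Φ(−z − 1.96).

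| Shift in p | RR | Relative rate | Change | Events of 137 | Rejection probability |
|---|---|---|---|---|---|
| none | any | unchanged | 0 | 0 | 5% |
| 0.40 to 0.35 | 2 | 1.40 to 1.35 | −3.6% | 4.9 | 6.0% |
| 0.40 to 0.35 | 3 | 1.80 to 1.70 | −5.6% | 7.6 | 7.6% |
| 0.40 to 0.30 | 2 | 1.40 to 1.30 | −7.1% | 9.8 | 9.4% |
| 0.40 to 0.30 | 3 | 1.80 to 1.60 | −11.1% | 15.2 | 16.4% |

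**3. A smaller case from a documented range.** The only higher-risk group that the protocol quantifies on these units is long-term care residents. Suppose their share moved across the whole 4.3-5.6% range between phases, admissions approximated patient-days, and RR were 3. The relative rate goes from 1 + 0.056 × 2 = 1.112 to 1 + 0.043 × 2 = 1.086. That is −2.3%, about 3 events, with a rejection probability of about 5.4%.

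**4. What the design features protect against.** The time series models level and trend, so gradual drift is handled. The withdrawal phase exposes a shift that does not reverse. Neither deals with a change that rises and falls with the phases. Baseline takes months 1-6, intervention months 7-12, and withdrawal starts two weeks later. Baseline and withdrawal therefore fall in roughly the same half of the calendar year and intervention in the other. A seasonal change in patients has the same on-off shape as a policy effect.

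**The case against.** The strongest reply is that a full adjustment set belongs in the statistical analysis plan, which is not at hand. The covariate sentence does not say that only these three will be used. That is fair, and a reader should not infer that the protocol forbids patient covariates. But the protocol does name and number what goes into the analysis, and a plan that followed it as written would contain no patient-mix term. So this is more than detail left for later.

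Other objections limit the point without removing it:

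- The design is not a bare before-after comparison. It would be wrong to say that no planned analysis can separate case mix from effect, because smooth trends and non-reversing shifts are covered. Phase-aligned changes are not.
- Calling all three covariates staff behaviour is too strong. Days of therapy is a risk factor for acquisition and partly tracks how ill patients are. It is still measured during the stay, not at admission.
- The same six units serve in every phase, so only shifts in patient-day share between units can confound.
- The earlier trial differed in design and setting, and that it ran in the same hospital is implied rather than stated. Different covariates there are not a contradiction. It serves as a benchmark for what the team has considered relevant.
- The 40% share, the 5 to 10 point shifts and the risk ratios of 2 to 3 have no source in the document. Even the largest case is 15 events against the 42 that the study is sized for.

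**Conclusion.** The point stands as an avoidable source of bias of unknown size. The named covariates leave case-mix changes that coincide with a phase unadjusted, and the plain phase comparison has no case-mix term.

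Under the assumed inputs, the crude rate moves by about 4% to 11%, and a crude two-period test rejects in about 6% to 16% of trials with no true effect, instead of 5%. These figures are illustrative. They rest on an assumed two-sided 0.05 level and independent Poisson counts, and they ignore the withdrawal phase and the time series. A reader might take 16% as the trial's actual false-positive rate, or conclude that a finding from Aim III would necessarily be confounded. The documents support neither: they give no data on how patient mix varies between half-years, and the one quantified group yields only about 5.4%.

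**What to change.** Add a fourth covariate group to Aim III: patient mix fixed at admission, consisting of age, a comorbidity measure and unit. Summarise it from hospital records per unit and half-month interval. Use it in a supplementary count model of the phase comparison, with a patient-day offset, unit terms and standard errors that allow for serial correlation. Keep the planned time series as it is, and report crude and case-mix-adjusted rate ratios side by side. Restricting the group to characteristics fixed at admission avoids adjusting for anything the intervention could change.

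The cost is protocol or analysis-plan wording, one data extraction and a few more model terms; no new patients or audits are needed. That the data can be obtained is an assumption, based on the adjustment in the earlier trial. Counts are sparse: 6 units × 12 intervals = 72 cells per period, and 137/72 = 1.9 events per cell. Unit-level averages give only aggregate control of confounding, and the report should say so.

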When they are admitted to acute care facilities, these patients become an important source of MDRO and C. difficile transmission. In a study evaluating the inter- and intradissemination of MDRGNB among LTCF residents with advanced dementia, genetically-related MDRGNB strains were detected in residents of 82% (18/22) of LTCFs indicating interdissemination between these facilities. The authors concluded that MDRGNB are spread both within and between LTCFs among residents with advanced dementia and that infection control measures should target this high-risk group of residents. A model of MRSA outbreaks in a LTCF demonstrated both direct and indirect effects of LTCF resident transfers on acute care facilities' MRSA prevalence indicating the role of transmission and need for hospitals to address LTCF in their infection control strategy. CRE can be spread extensively throughout a diverse healthcare facility network, highlighted nicely by the involvement of 14 acute care hospitals, 2 long-term acute care facilities, and 10 LTCFs during an outbreak in a single community. C. difficile shares similar risk factor and reservoir considerations as MDROs with the LTCF populations. Data suggest that C. difficile infection is endemic in LTCFs and remains largely uncontrolled despite numerous efforts to manage the issue. The incidence rate (2.3 cases/10 000 resident-days) and recurrence rate (1.0 case/10 000 resident-days) of C. difficile infection in LTCFs is comparable to that of acute-care hospitals.

At present, Contact Precautions are routinely employed in acute care facilities for patients colonized or infected with MDROs or *C. difficile*. The decision to place a patient into these precautions is often based on the results of clinical or surveillance cultures positive for these pathogens. Notably, this practice may only identify patients at a time point after they have potentially exposed HCP, staff, and other patients. In addition, surveillance cultures obtained on patient admission is a controversial infection prevention strategy and may not be performed in some hospitals. Even in those facilities that do perform such screening, testing for all important MDROs is rare and often not practical. Because of this, some have endorsed different

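### Aim III names no covariate for imported carriage, so a change in importation confined to the intervention phase could mimic or mask a policy effect

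*Protocol*

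**What the plan says.** The Covariates paragraph of Specific Aim III opens with "Several factors may affect the impact of the intervention on the primary outcome. These will be measured and included in the analysis". Three items follow:

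- "Study unit compliance with hand hygiene as monitored by the Vanderbilt Hand Hygiene Program";
- PPE compliance, for which "Trained study personnel will perform audits of PPE use by HCP caring for patients placed into the preemptive intervention";
- broad-spectrum antimicrobial use, in days of therapy.

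Neither this paragraph nor the rest of Aim III adjusts for imported carriage, admission prevalence or the number of long-term care facility (LTCF) admissions.

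The Aim's Significance section calls LTCFs reservoirs of these organisms and says of their residents: "When they are admitted to acute care facilities, these patients become an important source of MDRO and C. difficile transmission".

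Under Primary outcome, events are found through VIPER, described as "an HAI surveillance platform that monitors laboratory results in real time". There is no active surveillance, so only clinical cultures count, and "Events will be classified as HO if the specimen was collected >3 days after admission to VUH".

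Under Study procedures, all six units go through a 6-month baseline, a 6-month intervention, a 2-week washout and a 6-month withdrawal period at the same time. The Analysis paragraph compares the three phases and adds an interrupted time series with Newey-West errors on 12 points per period.

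**The concern.** The Aim rests on the idea that arriving carriers seed transmission, yet the named covariates describe only what staff and prescribers do after arrival. The PPE audit covers only patients under preemptive isolation, so it has no counterpart in the baseline or withdrawal phases.

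Importation can enter the primary outcome by two routes:

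- **Transmission.** More carriers on a unit give more opportunity for acquisition.
- **Classification.** A patient who arrived colonized and is first cultured on day 4 or later counts as hospital-onset even if nothing was transmitted.

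With no concurrent control unit, a phase that happens to receive fewer carriers would show fewer hospital-onset events under an inert policy. A phase that receives more would hide a real benefit. At stake is whether a difference between phases can be attributed to the isolation policy.

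**Working it through.** **Inputs from the Protocol (Aim III, Sample size considerations).** 4,952 patient-days per month; 29,710 per period; 4.6 hospital-onset events per 1,000 patient-days; 137 events per period; 80% power for a difference of 1.4 per 1,000, about 42 events.

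**Assumptions.** Two-sided 0.05, since the Protocol states no alpha. Let *f* be the share of hospital-onset events that scales with importation, and *x* the proportional fall in importation from baseline to intervention. The Protocol gives neither, so both are varied.

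**Step 1: the plan's own figures.** 4,952 × 6 = 29,712. 29,710 × 4.6/1,000 = 136.7 events. 29,710 × 1.4/1,000 = 41.6 events. For 137 against 95 events, z = 42/√(137 + 95) = 2.76, and power = Φ(2.76 − 1.96) ≈ 79%. A two-proportion calculation gives 78%. The stated 80% is reproduced to within 2 points.

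**Step 2: false reductions with no policy effect, baseline against intervention only.**

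Baseline events a = 136.7; intervention events b = a(1 − f·x); z = (a − b)/√(a + b); chance of a significant decrease = Φ(z − 1.96). The nominal value is 2.5%.

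| f | x | Fewer events | Rate shift per 1,000 | z | Chance of significant decrease |
|---|---|---|---|---|---|
| 0.25 | 10% | 3.4 | 0.11 | 0.21 | 4% |
| 0.25 | 20% | 6.8 | 0.23 | 0.42 | 6% |
| 0.50 | 10% | 6.8 | 0.23 | 0.42 | 6% |
| 0.50 | 20% | 13.7 | 0.46 | 0.85 | 13% |
| 1.00 | 10% | 13.7 | 0.46 | 0.85 | 13% |
| 1.00 | 20% | 27.3 | 0.92 | 1.74 | 41% |

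For example, with f = 0.5 and x = 20%: b = 136.7 × 0.90 = 123.0; z = 13.7/√259.7 = 0.85; Φ(−1.11) = 13%. The rows with f = 1 are an upper case. A rise in importation gives shifts of the opposite sign and would mask a benefit.

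**Step 3: what the withdrawal phase does.** Keep f = 1 and no policy effect, and suppose (the Protocol states no such rule) that an effect is claimed only if there is both a significant fall from baseline and a significant rebound on withdrawal. Simulated Poisson counts give:

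| Pattern of importation | x = 10% | x = 15% | x = 20% |
|---|---|---|---|
| Lower level persists into withdrawal | 1.4% | 1.8% | 2.2% |
| Dip confined to the intervention phase | 5% | 12% | 25% |

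If importation falls by the same step again in withdrawal, the chance is below 0.2%. The design therefore handles persistent and continuing drift; the exposure that remains is a shift confined to the intervention phase.

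**The case against.** The strongest reply is that the design already answers the concern. A drift that persists does not rebound on withdrawal, and a segmented time series can absorb a smooth trend. Step 3 bears this out for persistent drift. It does not cover a dip, or a rise, that lines up with the intervention months.

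Second, the size depends on inputs the Protocol does not supply. The Protocol itself names antibiotic use as a factor in acquisition, so full proportionality is not a central case. That stands, and is why a range is shown.

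Third, day 1-3 clinical positives are a poor view of the patients the Aim is about. Silent carriers are not cultured, and the Significance section says Contact Precautions are already routine for patients colonized or infected with these organisms. This also stands, and it limits what the covariate can remove. It weakens the control-series use less, although that series would also move with culturing practice.

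Fourth, the list may not be exhaustive, and further adjustment could sit in a statistical analysis plan. That is fair. But the Protocol itself names what goes into the analysis, and the factor its rationale points to is absent.

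A reader might infer more than the text supports: that any change in importation will be read as a policy effect, that the false-positive risk is simply 13% to 41%, or that VIPER collects day 1-3 positives and throws them away. The first ignores the withdrawal phase and the time series. The second is only the upper case on one contrast. The third is not stated: the Protocol says VIPER monitors laboratory results, and the hospital-onset rule needs each specimen's timing relative to admission. That early positives are available is thus a sound inference, not a documented fact.

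**Conclusion.** The concern holds in a limited form. The named covariates leave out imported carriage, which the Aim treats as a source of transmission, and there is no concurrent control to absorb a change in it. Persistent drift and smooth trends are reasonably guarded against; a shift confined to the intervention phase is not, and it could bias the result in either direction.

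On the baseline-intervention contrast, falls of 10% to 20% raise the chance of a false significant reduction from 2.5% to 4-6% at a 25% share, 6-13% at a 50% share, and 13-41% at a full share. These figures assume two-sided 0.05, Poisson counts, no policy effect, and illustrative values for the share and the fall. They show how sensitive the comparison is; they do not estimate the study's actual error rate. The study remains feasible as planned, but attribution of a difference to the policy would be weaker than it need be.

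**What to change.** From the laboratory feed that VIPER already monitors, count MDRO and *C. difficile* positives from specimens collected on days 1-3, per 100 admissions on the six units, by phase and by half-month to match the planned time points. Then:

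1. **Report the series across the three phases as a control outcome.** The unit policy has little way to change it, so a parallel fall would point to drift. This is the firmer part of the fix.
2. **Add the series to the time-series model as a covariate in a sensitivity analysis,** and show the phase effects with and without it.

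The sponsor should first confirm that the feed yields these positives with collection dates.

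The cost is one extra tabulation and one model term (one degree of freedom). Clinical cultures index importation only partly, miss silent carriers and vary with culturing practice. The adjustment should therefore be described as partial, and a flat control series should not be taken as proof that importation was stable.
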